**Table 5-1 Protocol deviation severity codes and analysis sets**

Protocol deviation severity code		Safety analysis set	PK analysis set	PD analysis set
Code	Text			
5	Exclude subject from all safety analysis	-	-	-
8	Exclude from all analyses	-	-	-
20	Exclude subject from PK analysis set	+	-	+
22	Exclude subject from PD analysis set	+	+	-
23	Exclude subject from PK and PD analysis set	+	-	-
49	Report relevant protocol deviation – include subject in all analysis sets	+	+	+

+ = include in analysis set, - = exclude from analysis set, NA = not applicable

## 6 Statistical methods for Pharmacokinetic (PK) parameters

### 6.1 Pharmacokinetic parameters

If data permits, the following pharmacokinetic parameters will be determined using the actual recorded sampling times and non-compartmental analysis: Cmax, Cmax,ss, Ctrough, Ctrough,ss and AUC's from the CFZ533 plasma concentration-time data. Concentrations below the LLOQ will be treated as zero for PK parameter calculations. The linear trapezoidal rule will be used for AUC calculation. Regression analysis of the terminal plasma elimination phase for the determination of T1/2 will include at least 3 data points after Cmax (but not including Cmax). If the adjusted R^2 value of the regression analysis of the terminal phase is less than 0.75, T1/2, AUCinf, Vz/F and CL/F will be excluded and indicated as missing values.

### 6.2 Analysis of pharmacokinetics

Plasma CFZ533 concentration data will be listed by cohort, treatment, subject, and visit/sampling time point. Descriptive summary statistics will be provided by cohort, treatment and visit/sampling time point, including the frequency (n, %) of concentrations below the LLOQ and reported as zero. Summary statistics will include mean (arithmetic and

geometric), SD, CV (arithmetic and geometric), median, minimum and maximum. Concentrations below LLOQ will be treated as zero in summary statistics. A geometric mean will not be reported if the dataset includes zero values.

Pharmacokinetic parameters will be listed by cohort, treatment and subject. Descriptive summary statistics will include mean (arithmetic and geometric), SD, and CV (arithmetic and geometric), median, minimum and maximum. An exception to this is Tmax where median, minimum and maximum will be presented.

Corporate Confidential Information

. During any modeling of PK data, the broad principles outlined in the FDA Guidance for Industry: Population Pharmacokinetics, will be followed.

## **7 Statistical methods for Pharmacodynamic (PD) parameters**

### **7.1 Analysis of the primary variable**

#### **7.1.1 Statistical model, hypothesis, and method of analysis**

The primary efficacy variable is the ESSDAI change from baseline.

It is assumed that the ESSDAI will follow an approximate normal distribution. If this assumption appears to not be met, alternative statistical methods may be applied. For example, data may be log transformed with changes from baseline in the log transformed data being analyzed.

The analysis of the data for the primary variable from Cohorts 1 and 2 differs from that proposed in the protocol in that it will not be conducted combining placebo data from those two cohorts. Being in two separate consecutive cohorts, one s.c. and the other i.v., they are not now considered similar enough to combine. As a result, the active treatments under consideration, Corporate Confidential Information are each compared to their respective matching placebo treatments within each cohort. Cohort 3 simply compares two alternative loading regimes.

For each of cohorts 1 and 2, a longitudinal model describing ESSDAI change from baseline over time will be fitted up to Week 13 with the following fixed effect terms: baseline ESSDAI, treatment group, visit, and interaction between treatment group and visit. In the first instance an unstructured variance-covariance matrix will be fitted; if there are issues with convergence then other variance-covariance matrices will be investigated. The change from baseline in ESSDAI at Week 13 (end of placebo-controlled period) will be estimated from the model. Inference will be done in the frequentist framework.

For Cohorts 1 and 2 the results from the primary analysis will be assessed against the following efficacy criteria:

- a statistically significant reduction in ESSDAI at Week 13 in the CFZ533 i.v. group compared to placebo, at the one-sided 10% significance level, and
- an estimated mean reduction in ESSDAI in the CFZ533 i.v. group to be 5 points or greater than placebo.

The decrease of 5 points was chosen because it is in the range of what was observed at week 12 in a small open-label study with rituximab ([Meiners et al 2012](#)). A positive sign of efficacy will be considered if both criteria are met.

In Cohorts 1 and 2, ESSDAI data after Week 13, where there is no longer a placebo treatment, will be examined similarly. It will also be summarized using descriptive statistics of both absolute values and changes from baseline and the raw data displayed graphically for individual patients and for visit treatment means. Graphs will also be used to display modelled treatment effects over time.

ESSDAI data from Cohort 3 up to Week 13 and then to Week 21 will also be analyzed in a similar way to the data from each of Cohorts 1 and 2, but with two active treatment groups instead of comparison with control. It will also be summarized with descriptive statistics and plots similarly.

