3.2 Rationale for study design

This study will be conducted in patients with active pSS for which no existing treatment has been proven effective against the underlying disease. Corporate Confidential Information

Cohorts 1 and 2

Two different doses Corporate Confidential Information of CFZ533 will be assessed in two separate cohorts.

A randomized, placebo-controlled, double-blind approach is used to eliminate potential bias in reporting safety and clinical efficacy data in this first, exploratory study in pSS patients. Patients will be randomized to CFZ533 or placebo in a 2:1 ratio in order to minimize exposure to placebo and to gather more data on CFZ533. Stratified randomization is done in order to limit imbalances between active and placebo arms in baseline intake of oral corticosteroids.

The open-label period will administer CFZ533 to all patients including those who were administered placebo in the placebo-controlled period. This would provide potential treatment benefit to these patients, and collect further safety and efficacy data for CFZ533 in pSS patients.

After the open-label period, patients will enter a follow up period for which a duration of 8 weeks (12 weeks after the last dosing with CFZ533) was chosen to allow sufficient time for monitoring safety and exploring duration of response.

In addition to safety, efficacy estimated by the EULAR Sjogren's Syndrome Disease Activity Index (ESSDAI) is chosen as a key endpoint of the study. The ESSDAI has been shown to be responsive in a retrospective analysis of a randomized controlled trial on rituximab, and was suggested to be a sensitive tool to assess efficacy of rituximab treatment (Moerman et al 2014). The authors reported a significant lower ESSDAI in the rituximab group compared to the placebo group at week 12 and week 24, demonstrating some effectiveness in reducing disease activity in this small study.

Cohort 3

Because of the key objective of this cohort, no placebo control is required, and open-label treatment is justified. In Cohort 3, two treatment arms are implemented to assess whether two loading regimens (multiple s.c. doses in treatment arm 1, or single i.v. administration in treatment arm 2), followed by a maintenance regimen (multiple s.c. doses, both arms), are set to 12 weeks (Day 1 to Day 85) to establish steady state conditions for CFZ533 concentrations in plasma at a level similar to trough concentrations observed in Cohort 2 Corporate Confidential Information

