9.4.2 Statistical model, hypothesis, and method of analysis

It is assumed that the ESSDAI will follow an approximate normal distribution. If this assumption appears to not be met, alternative statistical methods may be applied. These will be described full in the Reporting and Analysis Plan (RAP).

The analysis of the data for primary variable will be conducted combining data from both Cohorts 1 and 2. As a result, the three treatments under consideration would be Placebo (pooled), CFZ533 s.c. and CFZ533 i.v. A longitudinal model describing ESSDAI change from baseline over time will be fitted for the controlled part of the

study (up to Week 13) with the following covariates: baseline ESSDAI, baseline prednisone dose, treatment (three as mentioned above), time as a continuous factor and a quadratic time effect, as well as a random intercept, a random slope and a random quadratic effect for subject. An unstructured covariance matrix for the random effects will be fitted along with an independent error matrix. The change from baseline in ESSDAI at Week 13 (end of placebo-controlled period) will be estimated from the model for all treatments and the difference between treatments to placebo will be presented along with 80% confidence intervals. Inference will be done in the frequentist framework.

The results from the primary analysis will be assessed against the following efficacy criteria to support internal decision making (inference is done in the frequentist framework):

- a statistically significant reduction in ESSDAI at Week 13 in the CFZ533 i.v. group compared to placebo, at the one-sided 10% significance level, and
- an estimated mean reduction in ESSDAI in the CFZ533 i.v. group to be 5 points or greater than placebo.

The decrease of 5 points was chosen because it is in the range of what was observed at week 12 in a small open-label study with rituximab (Meiners et al 2012). A positive sign of efficacy will be considered if both criteria are met.

ESSDAI data after Week 12 will be summarized using descriptive statistics and displayed graphically. ESSDAI data from cohort 3 will also be summarized using descriptive statistics. More details will be described in the RAP.

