9.6 Sample size calculation

Cohorts 1 and 2

With 24 patients in the analysis of the primary efficacy variable (16 in the CFZ533 group and 8 in the placebo group), the study would have around 1% chance of having a false-positive result, i.e., of meeting both the efficacy criteria when the true difference between CFZ533 and placebo is zero. Additionally the chances of meeting both the efficacy criteria remain below 10% for true differences between CFZ533 and placebo of less than 2 points.

The study would have approximately 83% chance of meeting both the efficacy criteria, when the true difference between CFZ533 and placebo is 7 points.

In case the true difference between CFZ533 and placebo is only 5 points, the study would have approximately 51% chance of meeting both the efficacy criteria. These calculations assume that the primary efficacy variable, ESSDAI, follows a normal distribution with a standard deviation of 5. This estimate of the standard deviation is based on a study of rituximab in patients with primary Sjögren's syndrome (Meiners et al 2012) in which the observed standard deviation ranged from 5 at baseline to 3-7 post baseline.

With 24 patients (16 in the CFZ533 group and 8 in the placebo group), the study would have around 38% power (resp. 70% power) to detect an increase of 30% (resp. 42%) in the infection rate in the CFZ533 group, assuming a background rate of 5% on placebo.

The probabilities to observe a certain number of adverse events in each treatment arm, with this sample size, given assumed event rates, are given in [Table 9-1](#) below:

Table 9-1 Probability of observing a certain number of adverse events in the study given assumed underlying rates

Underlying true adverse event rate (in both treatment arms)	Probability to observe at least 4/16 patients with AEs on active arm	Probability to observe at least 2/8 patients with AEs on placebo	Probability to observe at least 8/16 patients with AEs on active arm	Probability to observe at least 4/8 patients with AEs on placebo
20%	0.402	0.497	0.007	0.056
35%	0.866	0.831	0.159	0.294
50%	0.989	0.965	0.598	0.637

The estimated difference in AE rates along with 90% confidence intervals, given a certain number of observed adverse events in each treatment arm, are given in [Table 9-2](#) below:

Table 9-2 Estimated difference in AE rates when observing a certain number of adverse events in the study

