## 2.2 Study design and treatment

This is a double-blind followed by open-label, randomized, placebo-controlled, parallel-group, non-confirmatory study to assess the safety, tolerability, pharmacokinetics, and preliminary clinical efficacy of multiple doses of CFZ533 in the following Cohorts 1 and 2:

- Cohort 1: CFZ533 administered subcutaneously in patients with pSS, in a doubleblind and placebo-controlled fashion, followed by open-label treatment;
- Cohort 2: CFZ533 administered by intravenous infusion in patients with pSS, in a double-blind and placebo-controlled fashion, followed by open label treatment.

These cohorts will be followed by an open label, randomized, parallel group, non-confirmatory part of Cohort 3:

- Cohort 3 (patients with pSS):  
In treatment arm 1 CFZ533 will be given at [redacted] s.c. weekly on 4 occasions (loading regimen), followed by [redacted] s.c. weekly on 9 occasions (maintenance regimen starting on study day 29). In treatment arm 2, the loading regimen will consist of a single i.v. dose of [redacted] CFZ533 (on study day 1), followed by [redacted] s.c. weekly on 12 occasions (maintenance regimen starting on study day 8).

[figure not shown]
The study will randomize approximately 68 patients with primary Sjögren's syndrome. In Cohorts 1 and 2, the randomization will be stratified by baseline intake of oral corticosteroids (yes/no). There will be no stratification in Cohort 3.

The study comprises three periods for Cohort 1 and Cohort 2:

- 1) placebo-controlled period (from Day 1, Week 1 to completion of pre-dose assessments on Day 85, Week 13), during which 4 doses of CFZ533 or placebo will be administered on top of the standard of care therapy, (e.g., low dose corticosteroid) that is necessary to treat pSS;
- 2) open-label period (from dosing on Day 85, Week 13 to completion of assessments on Day 169, Week 25), when all patients will receive 4 doses of open-label CFZ533 treatment, and
- 3) follow-up period (Weeks 25 – 32), when patients will be followed up without study medication.

An illustration of the study design for Cohorts 1 and 2 is provided in Figure 2-1.

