### **Supportive analysis**

The Bayesian analyses proposed in the protocol for the interim analysis of Cohort 1 will serve as supportive to the main frequentist analysis above when applied in a similar manner to Cohorts 1 and 2.

Two Bayesian posterior probabilities as follows will be calculated for Cohorts 1 and 2:

$$\Pr(\theta_{CFZ533,13w} - \theta_{\text{placebo},13w} < 0 \mid \text{data})$$

$$\Pr(\theta_{CFZ533,13w} - \theta_{\text{placebo},13w} < -5 \mid \text{data})$$

where  $\theta$  means change from baseline in ESSDAI at Week 13.

It is assumed that  $Y_{ijt}$ , the observed change from baseline in ESSDAI for subject  $i$  receiving treatment  $j$  (CFZ533 or placebo) at time  $t$ , follows a normal distribution  $N(\theta_{jt}, \sigma^2)$ . It is further assumed that  $\theta_{jt}$  follows a standard non-informative prior Normal distribution,  $p(\theta_{jt}, \sigma^2) = 1/\sigma^2$ .

This statistical model will be a repeated measures Bayesian analysis with baseline as a covariate using PROC MCMC. Example SAS code is provided in the RAP Module 8. Estimates of the difference between CFZ533 and placebo at each timepoint will be derived from this model and presented together with 95% credible intervals.

If required, further frequentist supportive analyses will attempt to model the time effect to better describe changes over time. If so, the model may include the following covariates: baseline, treatment, time, treatment by time interaction, treatment by time squared interaction, as well as a random intercept and a random slope for each patient. Time may be modeled as a continuous variable. The model may be simplified if there are problems with convergence, including a simpler variance-covariance matrix. The treatment by time squared interaction will be included if it improves the fit.

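### The SAP's primary ESSDAI model for Cohort 2 has no term for oral corticosteroid use, the randomisation stratum, and does not say that the protocol's prednisone adjustment was dropped

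*SAP*

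**What the plan says.** SAP 2.2 states: "In Cohorts 1 and 2, the randomization will be stratified by baseline intake of oral corticosteroids (yes/no"). Protocol 3.1 says the same, and Protocol 3.2 gives the purpose: "Stratified randomization is done in order to limit imbalances between active and placebo arms in baseline intake of oral corticosteroids".

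The primary model in Protocol 9.4.2 is fitted "with the following covariates: baseline ESSDAI, baseline prednisone dose, treatment (three as mentioned above"), plus time terms and subject random effects. The synopsis also lists prednisone dose.

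The SAP 7.1.1 model, fitted separately in Cohorts 1 and 2, is specified "with the following fixed effect terms: baseline ESSDAI, treatment group, visit, and interaction between treatment group and visit". Neither supportive model restores the adjustment. Of the Bayesian one the SAP says: "This statistical model will be a repeated measures Bayesian analysis with baseline as a covariate using PROC MCMC". Of the frequentist one: "the model may include the following covariates: baseline, treatment, time, treatment by time interaction, treatment by time squared interaction".

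SAP 7.1.1 does have a statement of departures. It says the analysis "differs from that proposed in the protocol in that it will not be conducted combining placebo data from those two cohorts", and it gives a reason for that change alone.

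**The concern.** The design restricts randomisation on a factor and the protocol adjusts for a version of it. The SAP then drops both versions without comment. Un-pooling placebo does not explain the removal, and a reader of SAP 7.1.1 would assume that the steroid adjustment still stands.

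Stratifying makes the arms alike on steroid use, so the real sampling variance of the treatment difference falls if steroids matter. A model without the stratum leaves that variation in the residual and reports too large a standard error. At stake are the Cohort 2 Week 13 interval and the significance test, which is one of the two efficacy criteria. The supportive Bayesian probabilities are affected slightly.

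**Working it through.** **Inputs from the documents.** 24 analysed, 16 against 8, with an outcome that "follows a normal distribution with a standard deviation of 5" (Protocol 9.6); 30 randomised and about 24 completing in Cohort 2 (Protocol 3.1); one-sided 10% test and an estimated difference of at least 5 points (SAP 7.1.1).

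**Assumptions.** The documents give neither the share on steroids nor the difference in ESSDAI change between strata after baseline adjustment (the gap). I took shares of 50%, 30% and 15%, and gaps of 0, 2.5 and 5 points. Residual SD is 5, baseline ESSDAI has SD 5 and is independent of stratum, and loss is random. Protocol 1.1 calls glucocorticoids mostly ineffective in this disease, so a gap of 5 (one residual SD) is an upper case.

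**1. The plan's own figures.** SE = 5 × √(1/16 + 1/8) = 2.165. The chance that the estimate reaches 5 is 1 − Φ((5 − δ)/2.165):

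| True difference δ | Computed | Protocol 9.6 |
|---|---|---|
| 0 | 1.05% | around 1% |
| 2 | 8.3% | below 10% for less than 2 |
| 5 | 50.0% | about 51% |
| 7 | 82.2% | about 83% |

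They reproduce, with no covariate. The t test on 22 df needs an estimate of only about 1.321 × 2.165 = 2.86 points, so the 5-point rule decides.

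**2. Mechanism.** With share p and gap g, the residual variance without the term is 25 + p(1 − p)g². For p = 0.5 and g = 5 this is 25 + 6.25 = 31.25, an SD of 5.59 instead of 5. With balanced strata the extra part inflates the model SE but not the true variability of the estimate.

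**3. Cohort 2, Week 13 linear model.** 20,000 simulated trials per setting: stratified 2:1 allocation in blocks of 3, 6 of 30 lost at random, half on steroids. Each pair is without / with the stratum term.

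| Gap | 80% interval coverage | Test size | Power at a true 3 points |
|---|---|---|---|
| 0 | nominal | nominal | 51.5 / 51.1% |
| 2.5 | 81.1 / 80.0% | 9.4 / 9.9% | 49.8 / 51.1% |
| 5 | 83.8 / 80.0% | 8.1 / 9.9% | 45.3 / 51.1% |

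At gap 0 the SE is 2.205 / 2.217 (2.217/2.205 = 1.005). At gap 5 without the term, the model SE is 2.48 against a true SD of 2.30, and the mean 80% interval width is 6.57 / 5.88.

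Both efficacy criteria met, gap 5: 1.4 / 1.2% (true 0), 19.5 / 18.8% (true 3), 49.9 / 49.9% (true 5), 80.9 / 81.2% (true 7).

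**4. Other shares, power at 3 points.** With 30% on steroids: 49.8 / 50.9% (gap 2.5) and 46.1 / 50.9% (gap 5). With 15%: 50.2 / 50.4% and 48.0 / 50.4%; the SE cost at gap 0 is 1.0%.

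**5. Repeated-measures model as in the SAP.** Four post-baseline visits, unstructured covariance, assumed visit correlation 0.6, 30 analysed with 6 leaving early; 2,500 trials per setting, Monte Carlo error about 1 point. Gap 0: SE +0.1%. Gap 2.5: coverage 81.7 / 80.2%, power at 3 points 52.8 / 54.4%. Gap 5: coverage 84.5 / 80.2%, size 7.7 / 10.2%, power 48.8 / 54.4%, both criteria at a true 5 points 50.1 / 50.2%. The fits converged under the algorithm used; other software was not tested.

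**6. Stratum or dose.** If the effect is proportional to dose, with users spread evenly over 2.5, 5, 7.5 and 10 mg (assumed, within the protocol's limit), power at 3 points with no term / stratum / dose is 49.5 / 50.7 / 51.1% (mean gap 2.5) and 43.4 / 48.9 / 51.1% (mean gap 5).

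**7. Bayesian analysis (flat-prior t approximation), gap 5.** Mean Pr(difference < 0) at a true 3 points is 0.81 / 0.82; the 95% interval covers 96.4 / 94.9%.

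**8. Cohort 1, 10 analysed.** Mean 80% interval width, half on steroids: 9.99 / 10.36 at gap 0 (+3.7%), 10.36 / 10.36 at gap 2.5, 11.40 / 10.36 at gap 5. With 30% on steroids the change is +4.8%, +1.5% and −7%.

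**The case against.** **No decision changes.** Efficacy is called positive only if both criteria are met, and that chance is the same with or without the term. This stands. The loss falls on the interval and the significance test, and power at 3 points concerns an effect below the 5-point bar.

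**The gap is undocumented and probably small.** This stands too. Entry doses are capped and stable, and baseline ESSDAI is already in the model. At 2.5 points the loss is about 1 percentage point, and the error is conservative.

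**SD 5 is used as a residual SD, though the protocol gives it for the outcome.** Fair: adding a 5-point gap raises the total SD to 5.59. With the total held at 5, power at 3 points is 51.6% without the term and 59.5% with it. There is then no shortfall against the plan, but the model still gives up available precision and the test is still conservative.

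**SAP 1.2 treats a change of statistical model as minor.** It allows such a change to be recorded in a note to file, an addendum or the study report, and those and Module 8 are not visible. The point about non-declaration is therefore limited to the visible text. SAP 7.1.1 nevertheless declares one departure and is silent on this one.

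**Interim analyses have already occurred (SAP 3), so a new term needs justification.** It does. A randomisation factor close to the protocol's own covariate is easy to justify. An unexplained removal in an SAP written after interim analyses invites the same question.

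**Absence of bias assumes random loss.** Correct. Unequal dropout can shift one trial's estimate: steroid users 5/8 on placebo and 7/16 on active differ by 0.19, which at an assumed 4-point effect is about 0.75 points. That favours the term.

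**Conclusion.** The concern holds. The visible SAP text removes the protocol's steroid adjustment from the primary and supportive models, leaves out the randomisation stratum, and does not say so.

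The statistical consequence is modest and depends on an association the documents do not quantify. In Cohort 2 with half on steroids, it runs from nothing (gap 0) through about 1 percentage point of power at a true 3-point effect (gap 2.5) to about 6 (gap 5, an upper case), where the nominal 80% interval covers about 84% and the nominal 10% test has a size of about 8%. False positives are not inflated, the estimate is unbiased under random loss, and the go decision is essentially unaffected. The case for the change is that the term costs almost nothing in Cohort 2 and that readers should be told what was removed.

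**What to change.** **Cohort 2.** Add the oral corticosteroid stratum (yes/no) as a fixed effect to the primary ESSDAI model and to the matching Bayesian model. If the fit does not converge, simplify the covariance matrix first, as the SAP already allows, and keep the term.

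**Declaration.** In SAP 7.1.1, next to the un-pooling statement, say that the stratum replaces the protocol's baseline prednisone dose, and why. The same sentence can note that the protocol's quadratic time and random effects gave way to visit and an unstructured covariance.

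**Cohort 1.** Keep the SAP model as the main analysis and report the stratum-adjusted model as a sensitivity analysis, because with about 10 patients the term would widen the interval by about 4–5% if steroids are not prognostic.

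**If the omission in Cohort 2 is deliberate,** state that and report the adjusted model as a sensitivity analysis.

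**Cost.** One degree of freedom in Cohort 2, about 0.5% in SE if steroids are not prognostic (1.0% if only 15% use them), a short written justification, and no new data.
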